3.3 Criteria for Premature Termination of the Study: Stopping Rules

Study enrollment will be suspended pending expedited review of all pertinent data by the NIAID DSMB if the following occurs:

• Any death related to Baked Egg or Egg OIT dosing.
- More than 1 severe anaphylactic reaction (see Appendix 3) related to Baked Egg or Egg OIT dosing at any stage of the protocol.
- More than 3 treatment-related non-anaphylaxis severe adverse events (including EoE).
- More than 1 serious suspected adverse reaction occurs (serious and related).
- More than 3 subjects who require more than 1 injection of epinephrine for a single study product related allergic reaction during the study therapy.

4. Selection and Withdrawal of Subjects

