4.2 Exclusion Criteria

Subjects who meet *any* of these criteria are not eligible for enrollment as study subjects:

- History of anaphylaxis to egg resulting in hypotension, neurological compromise or mechanical ventilation.
- Chronic disease (other than asthma, atopic dermatitis, rhinitis) requiring therapy (e.g., heart disease, diabetes).
- Active eosinophilic gastrointestinal disease in the past 2 years.
- Participation in any interventional study for the treatment of food allergy in the past 6 months.
- Subject is on "build-up phase" of immunotherapy (i.e., has not reached maintenance dosing). Subjects tolerating maintenance allergen immunotherapy can be enrolled.
- Severe asthma (2007 NHLBI Criteria Steps 5 or 6, see Appendix 2).
- Mild or moderate (2007 NHLBI Criteria Steps 1-4) asthma with any of the following criteria met:
 - FEV1 <80% of predicted, or FEV1/FVC <75%, with or without controller medications (only for age 6 or greater and able to do spirometry), or
 - ICS dosing of >500 mcg daily fluticasone (or equivalent inhaled corticosteroids based on NHLBI dosing chart), or
 - 1 hospitalization in the past year for asthma, or
 - 1 ER visit in the past 6 months for asthma.
- Use of steroid medications (IV, IM or oral) for asthma in the following manners:
 - history of daily oral steroid dosing for >1 month during the past year, or
 - o burst or steroid course in the past 3 months, or
 - \circ >2 burst oral steroid course in the past year.

- A burst of IV, IM or oral steroids of more than 2 days for an indication other than asthma in the past 30 days.
- Inability to discontinue antihistamines for the initial day of escalation, skin testing or OFC.
- Use of omalizumab or other non-traditional forms of allergen immunotherapy (e.g., oral or sublingual) or immunomodulator therapy (not including corticosteroids) or biologic therapy (e.g., infliximab, rituximab, etc.) within the past year.
- Use of β-blockers (oral), angiotensin-converting enzyme (ACE) inhibitors, angiotensinreceptor blockers (ARB) or calcium channel blockers.
- Use of investigational drug within 90 days or plan to use investigational drug during the study period.
- Pregnancy or lactation.

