4.3 Premature Subject Termination from the Study

4.3.1 Criteria

No subject initiating therapy in this trial will be replaced.

Any subject may be prematurely terminated from additional allergen exposures, but maintained on longitudinal follow-up for the following reasons:

• Anaphylaxis resulting in hypotension, neurological compromise or mechanical ventilation secondary to Baked Egg or Egg OIT dosing or any egg food challenge.

Any subject deemed to have severe symptoms and receives aggressive therapy at any time should be discontinued from further therapy, including the following:

- Poor control or persistent activation of secondary atopic disease (e.g., AD, asthma).
- Started on ARBs, ACE inhibitors, beta-blockers, or other prohibited meds and there are no alternative meds available per the prescribing doctor, they will be removed from further treatment.
- Pregnancy.
- Egg OIT Group subjects:
 - Circumstances (e.g., concurrent illness, such as gastroenteritis) requiring missed Egg OIT maintenance dosing of >7 consecutive days (this does not include subjects intentionally removed from therapy to administer an OFC off therapy).
 - Non-adherence with home Egg OIT dosing protocol (excessive missed days; i.e., >3 consecutive days missed on 3 occasions), would be a safety issue warranting discontinuation.

Any subject may be prematurely terminated from the study if:

- The subject elects to withdraw consent from all future study activities, including followup.
- The subject is "lost to follow-up" (i.e., no further follow-up is possible because attempts to reestablish contact with the subject have failed).
- The subject has biopsy documented Eosinophilic Esophagitis (EoE).

• The subject dies.

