4.3.2 Follow-up of Subjects Who Discontinue Treatment Only

Subjects who prematurely discontinue treatment with Baked Egg or Egg OIT will remain in the study until normal termination. All willing subjects will be followed for the duration of the study to monitor safety and efficacy parameters, and they will be contacted annually by telephone for long term follow-up through September 30, 2018.

5. Study Medication

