then will return every 2 weeks to the Clinical Research Center for single dose escalation until a dose of 25 mg is achieved using the following dose escalation scheme: 3 mg to 6 mg to 12 mg to 25 mg. Subjects will be called 1 week after each dose escalation visit to assess for dosing compliance and dose reactions. Subjects should withhold their daily home dose on the escalation day but should take all other scheduled medications. Note that the daily home dose should be taken as part of a meal. It is recommended that the dose be taken at a consistent time (within a 4 hour time period), and it is critical to take the dose every day. Doses should be separated by at least 12 hours. Subjects who require dosing reduction during the 2 week period will reset their 2 week escalation schedule to maintain the new dose for a 2 week period prior to attempting to escalate again. After tolerating 25 mg egg white solid, the subject will continue dose escalations every 2 weeks. Any dose escalation attempts may be postponed for 1-2 extra weeks based on clinical judgment. An escalation attempt must be made by 4 weeks, unless escalation is delayed due to administration of epinephrine as defined in Section 6.4.1. Failure to successfully escalate for 3 consecutive attempts will result in the subject being withdrawn from further therapy. The subject will be followed for the remainder of the study for safety and immunologic monitoring. (See schedule for initial day dose escalation, Section 6, Exhibit 1) A physician will be available at all times during any of the Clinical Research Center Egg OIT dosing visits.

Any subject who discontinues escalation dosing due to repeated allergic reactions to the egg product will have his/her mechanistic blood drawn within approximately 1 week of discontinuation of therapy.

Subjects may have clear liquids and JELL-O during the day of the initial day escalation protocol while they are being given the desensitization doses.

Reactions to Egg OIT During Initial Escalation:

Process algorithm for symptoms during the initial escalation protocol. (See Section 6, Exhibit 1)

Subjects may develop symptoms during the initial escalation protocol, similar to those seen during other desensitization protocols (e.g., venom immunotherapy, drug desensitization). The investigator's judgment will be required to determine the best course of action with possible actions being the following: Extension of time interval between dosing (additional 30 minutes).

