7.4.2 SAE Recording and Reporting Procedures

Serious AEs will be recorded on the SAE CRF and health authorities will be notified as outlined in Section 7.5.2. All centers are obligated to report SAEs within 24 hours of their occurrence and/or the sites knowledge of the event to the SACCC. The following attributes will be assigned:

- Description
- Date of onset and resolution (if known when reported)
- Severity
- Assessment of relatedness to test article
- Action taken

The site investigator will apply his/her clinical judgment to determine whether an adverse event is of sufficient severity to require that the subject be removed from treatment. If necessary, an investigator will suspend any trial procedures and institute the necessary medical therapy to protect a subject from any immediate danger.

Subsequent review by FDA, the DSMB, ethics review committee or IRB, or the sponsor(s) may suspend further trial treatment or procedures at a site. The study sponsor(s), FDA and DSMB retain the authority to suspend additional enrollment and treatments for the entire study as applicable.

A subject may voluntarily withdraw from treatment due to what he/she perceives as an intolerable AE, or for any other reason. If voluntary withdrawal is requested, the subject should

be asked to continue (at least limited) scheduled evaluations, and the study staff will complete a dosing termination form, and the subject will be given appropriate care under medical supervision until the symptoms of any AE resolve or their condition becomes stable.

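### Biopsy-documented EoE is listed only as a reason to end study participation, so a willing child may lose scheduled visits and capture of later SAEs

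*Protocol*

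**What the plan says.** Protocol 4.3.1 separates stopping exposure or therapy from leaving the study. The first list opens "Any subject may be prematurely terminated from additional allergen exposures, but maintained on longitudinal follow-up for the following reasons" and holds anaphylaxis with hypotension, neurological compromise or ventilation. Further reasons for stopping therapy follow. The last list opens "Any subject may be prematurely terminated from the study if" and has four entries: consent withdrawn from all activities, loss to follow-up, EoE ("The subject has biopsy documented Eosinophilic Esophagitis (EoE") and death.

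Section 4.3.2, whose title limits it to subjects who discontinue treatment only, keeps them in the study to normal termination: "All willing subjects will be followed for the duration of the study to monitor safety and efficacy parameters". It also provides annual telephone contact.

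Eosinophilic disease appears in two other rules. The stopping rule in 3.3 counts "More than 3 treatment-related non-anaphylaxis severe adverse events (including EoE"), and 4.2 excludes "Active eosinophilic gastrointestinal disease in the past 2 years". Neither says what happens to the follow-up of an enrolled child who develops EoE.

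**The concern.** In three of the four study-termination entries, follow-up is refused or impossible. EoE is different: the child is alive and can be contacted, and the family may be willing. The protocol treats other stops differently, and nothing in it explains why EoE should be the exception.

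EoE is also a possible treatment harm, and the only non-anaphylaxis harm named in the 3.3 stopping rule. A child taken off study for it leaves for a reason that may be related to treatment. Any safety data lost afterwards would not be lost at random, and the trial is unblinded and compares SAE incidence between groups. Because the wording is permissive, two sites could handle the same diagnosis differently: one stops dosing and keeps the child, the other ends participation.

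**Working it through.** **Step 1. Compare how the protocol handles other stops.**

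- Hypotensive anaphylaxis (4.3.1): exposure ends, longitudinal follow-up is kept.
- Three failed escalations (6.4, Egg OIT initial dose escalation): "The subject will be followed for the remainder of the study for safety and immunologic monitoring".
- More than 7 consecutive missed days, or repeated long gaps (6.4, missed Egg OIT doses): therapy stops, the child is followed longitudinally.
- Voluntary withdrawal from treatment over an intolerable AE (7.4.2): the subject should "be asked to continue (at least limited) scheduled evaluations, and the study staff will complete a dosing termination form".
- Biopsy-documented EoE (4.3.1): named only under study termination.

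**Step 2. Separate what survives termination from what may not.**

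- The EoE event is recorded as an AE. Section 7.2.1 follows it to resolution or to 30 days after study termination. Section 7.4 uses resolution, stability, or 30 days after study treatment is completed. Section 7.4.1 has the investigator observe the child until symptoms resolve or stabilize, with no time limit. The end points differ, but follow-up of the event is provided for.
- A new SAE after termination is the gap. Section 7.2 plans safety reporting up to Visit 08, but no text clearly applies this to a child already off study.
- The annual calls are described for all subjects (6.4, 11.2, Appendix 1 footnotes). Under 7.2 they collect no safety events other than food allergy episodes, so they do not replace SAE capture.

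**Step 3. Count the visits at risk.** Weeks come from Appendices 1.A and 1.B. Later visits are those after the termination visit, up to and including Visit 07. Weeks remaining = 104 − week of termination.

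| Terminated at | Week | Later visits, Egg OIT | Later visits, Baked Egg | Weeks to Visit 07 |
|---|---|---|---|---|
| Visit 02 | 12 | 5 | 6 | 104 − 12 = 92 |
| Visit 03 | 24 | 4 | 5 | 104 − 24 = 80 |
| Visit 04 | 52 | 3 | 3 | 104 − 52 = 52 |
| Visit 05 | 68 | 2 | 2 | 104 − 68 = 36 |
| Visit 06 | 84 | 1 | 1 | 104 − 84 = 20 |

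Baked Egg has one more visit in the first two rows because its schedule adds a Month 9 assessment, which covers adverse events. Egg OIT dosing visits are left out because they end with dosing anyway. Visits 04 and 07 count for their non-challenge procedures only. Visit 08 is left out because it requires a passed on-therapy challenge. Starting at Visit 02 is an assumption; earlier termination would forgo Visit 02 as well.

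**Step 4. Size one missed event.** Protocol 9.3 randomizes 96 at 1:1, so 96/2 = 48 per arm; the assigned group is about 40. SAP 9.2 estimates the proportion of participants with an SAE. One unrecorded first SAE changes it by 1/48 = 2.1 points or 1/40 = 2.5 points.

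**Step 5. Check the primary endpoint and power.** The plan states 85% power for 40% against 70%, two-sided 5%. With 48 per arm and pooled rate 0.55, the null standard error is √(2 × 0.55 × 0.45/48) = 0.1016 and the alternative standard error is √((0.24 + 0.21)/48) = 0.0968. Then (0.30 − 1.96 × 0.1016)/0.0968 = 1.04, which gives power 0.851, so the stated figure reproduces. Under SAP 3.3 a child without the off-therapy challenge is a failure whether terminated or only off dosing, so neither the endpoint nor the power changes.

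**The case against.** The strongest reply is that the protocol already keeps the child by default. The EoE bullet only permits termination, whereas 4.3.2 says that subjects who stop treatment stay in the study. The harm needs an EoE case, a site that chooses termination for a willing family, a later first SAE, and failure to record it. The documents give no probability for any of these. Active eosinophilic gastrointestinal disease in the past 2 years is excluded and no endoscopy is scheduled. SAP 6.3 lets the safety population vary by period, and SAP 9.2 may omit testing if SAEs are rare. An EoE event already classed as serious would already count. All of this stands, and it keeps the point small. It does not explain why this one harm carries an option to end follow-up.

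A reader might infer more than the text supports:

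- **That EoE itself goes unfollowed once the 30 days in 7.2.1 have passed.** Section 7.4.1 has no such limit, and 7.4.2.1 expects SAE follow-up reports to include a resolution date.
- **That the annual calls are lost.** The wording covers all subjects and states no exception for those terminated.
- **That the 3.3 stopping count is affected.** The EoE event is recorded before any termination.

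**Conclusion.** The point holds as a modest, conditional gap in safety follow-up. If a site uses the study-termination option for EoE, a willing child may lose up to 5 (Egg OIT) or 6 (Baked Egg) scheduled visits after Visit 02, falling to 1 after Visit 06, and a later new SAE may go unrecorded. The visit counts are upper bounds that assume the child would otherwise have attended to Visit 07. The 2.1 and 2.5 point shifts assume planned group sizes, no earlier SAE in that child, and that the child stays in the denominator. The expected number of cases cannot be derived from the documents and may be zero. This is a weakness in a design choice, not an error in the sample size or the primary analysis.

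**What to change.** Move the EoE bullet in 4.3.1 from the study-termination list to the list that ends additional allergen exposures, egg challenges included, and keeps longitudinal follow-up. Section 4.3.2 then applies to willing children, with its annual calls, so no separate sentence on the calls is needed. The differing AE end points in 7.2.1, 7.4 and 7.4.1 concern every subject and need not be reworded for this purpose.

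The cost is one moved bullet and, on the Visit 02 assumption, up to 5 (Egg OIT) or 6 (Baked Egg) already-scheduled visits per case. It adds no new procedure and no further egg challenge. With no endoscopy in the schedule, the course of EoE would be judged from history, examination and medical records. Families can still withdraw consent, and clinical care of EoE stays with the investigators.

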4.3.2 Follow-up of Subjects Who Discontinue Treatment Only

Subjects who prematurely discontinue treatment with Baked Egg or Egg OIT will remain in the study until normal termination. All willing subjects will be followed for the duration of the study to monitor safety and efficacy parameters, and they will be contacted annually by telephone for long term follow-up through September 30, 2018.

5. Study Medication

5.1 Formulation, Packaging and Labeling

Study drug (commercially available egg white solid) will be centrally packaged, stored and distributed by EMINENT Services Corporation. Central manufacturing will consist of weighing individual doses of the egg white solid into vials or capsules and providing bulk egg white solid for use with scoops. A 37% egg white solid blended product as described in the manufacturing section of the IND will be used to provide specified dose levels as outlined in the dosing table in Section 3.0.

Initial day dose escalation will be packaged in individual vials with each dose weighed. Initial day escalation kits will have 2 doses of each vial up to 25 mg egg white solid. Individual dose level kits will have 21 vials per kit. Kits will be used until a dose of 50 mg egg white solid is achieved. Starting at doses of 50 mg, the egg white solid doses will be packaged in pull-apart capsules with the appropriate dose in each capsule. One capsule will be used for each day's dose. Capsules will be packaged in bottles of 21.

Starting at doses of 350 mg egg white solid, bulk powder will be dispensed with a dose-specific scoop. Subjects will be instructed to use 1 scoop per day that is leveled across the top of the scoop. The bulk product will be in a supply of 500 gm.

All study product will be packaged at the central manufacturer. Study drug will be shipped by the central manufacturer to the site pharmacist for distribution to the site study personnel. The site pharmacist will dispense study drug in a manner consistent with the current dose level and treatment assignment.

All study drug will be labeled at the central manufacturer and shipped to the local pharmacy for distribution to the study subjects. The product will be labeled with the numbered dose level and package number.

Every attempt to use a single lot of commercially available egg white solid will be made. If a new lot is required, and any subject is in an escalation phase of the study, they will have a single observed in clinic dose reduction with the new lot. Escalation to their previous dose may occur in 1 week if the subject has the same or fewer symptoms than those occurring with the previous lot.

5.2 Preparation, Administration and Dosage

The egg white solid will be provided pre-packaged from the site pharmacy in appropriate doses or in bulk with appropriate scoops to deliver the specified dose as outlined in Section 3. The egg white solid may be added to apple juice, applesauce, yogurt, pudding or other age-appropriate food. The product must be consumed promptly after mixing. If there is a delay in consumption, the product will be discarded and a new product dose mixed and consumed. Subjects will be given an adequate supply for the interval between scheduled visits with an additional 1 week supply to be used in the event of missed or cancelled study visits. Every attempt will be made to administer the dose of study drug at the same time of the day, each day. A target of at least 12 hours will pass between doses.

5.3 Drug Accountability

Under Title 21 of the Code of Federal Regulations (21CFR §312.62) the investigator is required to maintain adequate records of the disposition of the investigational agent, including the date

and quantity of the drug received, to whom the drug was dispensed (subject-by-subject accounting) and a detailed accounting of any drug accidentally or deliberately destroyed.

Records for receipt, storage, use and disposition will be maintained by the study site. A drugdispensing log will be kept current for each subject. This log will contain the identification of each subject and the date and quantity of drug dispensed.

All records regarding the disposition of the investigational product will be available for inspection by the clinical trial monitor.

5.4 Baked Egg Therapy

Baked Egg therapy will be prepared using commercially available food ingredients and prepared according to pre-specified recipes, cooking temperatures, and times to administer consistent doses of baked egg.

Baked Egg therapy will consist of a muffin or equivalent (1/3 of egg in serving or approximately 2 gm of protein).

Home baked products will have no more than 2 eggs per batch of recipe (yield 6 servings). Serving size is indicated by the yield of the recipe. Products will be baked for 25-50 minutes at 325-425 degrees Fahrenheit. Recipes will be provided. The daily dose can be administered at 1 sitting or divided throughout the dosing day.

These methods will be outlined in the manual of procedures and instructions for the subjects and their families.

5.5 Assessment of Compliance with Study Treatment and Monitoring

Families will document daily dosing and any reaction from at-home dosing by diary logs. Central monitoring of compliance will be performed. Families will be provided with 24 hour emergency contact information from each site.

All study medication will be brought back to the clinic with each visit for reconciliation of remaining vials, capsules or bulk powder. The bulk powder will be weighed at each clinic visit to assess that study product is being used but cannot assess the actual dose delivered on a daily basis.

5.6 Modification of Study Treatment

As described in the protocol, Egg OIT doses may be adjusted by the study physician if the subject is unable to tolerate the scheduled dose increase.

5.7 Concomitant Medications

All subjects may continue their usual medications, including those taken for asthma, allergic rhinitis and atopic dermatitis, during the study. However, they must be able to discontinue antihistamines prior to the initial day of escalation, skin testing and oral food challenges. Regular topical steroids use is permitted at the time of skin testing.

5.8 Prophylactic Medications

None

5.9 Rescue Medications

Treatment of individual allergic reactions during Baked Egg or Egg OIT therapy should be with either an antihistamine and/or epinephrine, along with IV fluids, albuterol and steroids as indicated. Subjects and parents are likely to have EpiPens®, but for those who do not, EpiPens® or an equivalent device will be provided. Subjects and parents will be trained in proper use and will be able to demonstrate proper technique with the EpiPen® or its equivalent.

